
Group 1. Basal bolus with glargine U300 once daily and glulisine insulin before meals (n=90).

Group 2. Basal bolus with glargine U100 once daily and glulisine insulin before meals (n=90).

IV.d. Basal Bolus Insulin Protocol.

Patients will be treated with a basal bolus insulin regimen as previously reported (15, 16, 39). In brief, subjects treated with insulin prior to admission will receive 80% of the total daily outpatient insulin dose given. Insulin naïve patients will discontinue oral agents and will receive a starting total daily dose (TDD) of 0.4 U/kg/day for BG between 140 mg/dl and 200 mg/dL and 0.5 U/kg/day for BG between 201 mg/dl and 400 mg/dL. The starting TDD will be reduced to 0.3 U/kg/day in patients \geq 70 years or with a GFR < 60 ml/min. Both groups will be treated with bolus regimen given half of TDD as basal (glargine U300 or U100) once daily and half as insulin glulisine divided in three equal doses before meals. Patients with poor oral intake or to be kept NPO will receive the basal dose, but prandial dose will be held (32). Insulin dose will be adjusted daily to maintain a fasting and pre-dinner BG between 80 mg/dl and 180 mg/dl.

IV. e Treatment randomization. This is an open label randomized controlled trial. Patients will be randomized 1:1 consecutively using a computer generated randomization table provided by [name], statistician at the Emory School of Public Health. The randomization table will be mailed to the research pharmacist at each institution who will be in charge of the randomization and group assignment. A research pharmacist at each institution will follow a computer-generated block randomization table based on prior insulin use (yes/no).

IV.f TREATMENT PROTOCOL - Basal Bolus Insulin Regimen with Glargine Once Daily plus Glulisine before Meals

Patients Treated with Insulin Prior to Admission

- Discontinue oral antidiabetic drugs on admission.

Subjects treated with insulin prior to admission will receive 80% or 100% of the total daily dose (TDD) given as basal bolus regimen. **Starting Insulin Doses:**

- Randomization BG <200mg/dl-give 80% of the TDD*
- Randomization BG>200mg/dl-give 100% of the TDD*
- Half of TDD will be given as basal (glargine U300 or U100) and half as rapid-acting insulin.
- Glargine U300 and U100 will be given once daily, at the same time of the day.
- Patients will receive the full-dose of glargine (even if NPO) the day of surgery or diagnostic procedure(s).

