- Glulisine insulin will be given in three equally divided doses before each meal. To prevent hypoglycemia, if a subject is not able to eat, glulisine insulin dose will be held.

* If patient was on basal only therapy consider adding prandial dose as calculated above.

Insulin Naïve Patients Treated with Oral Agents or GLP1-RAs Prior to Admission

- Discontinue oral antidiabetic drugs on admission.
- Starting total daily insulin dose:
 - 0.4 U/Kg/day when randomization BG between 140-200 mg/dL
 - 0.5 U/Kg/day when randomization BG between 201-400 mg/dL
 - Reduce TDD to 0.3 units per kg in patients ≥ 70 years of age and/or with an eGFR < 60 ml/min.
- Half of TDD will be given as glargine U300 or U100 and half as glulisine.
- Glargine will be given once daily, at the same time of the day.
- Patients will receive the full-dose of glargine insulin (even if NPO) the day of surgery or diagnostic procedure(s).
- Glulisine insulin will be given in three equally divided doses before meals. To prevent hypoglycemia, if a subject is not able to eat, the dose of glulisine will be held.

Supplemental insulin. Glulisine insulin will be administered following the “supplemental/correction insulin scale” protocol (Appendix 1).

- If a patient is able and expected to eat most of his/her meals, supplemental insulin will be administered before meals and at bedtime following the “usual” dose of the insulin scale protocol.
- If a patient is not able to eat, supplemental insulin will be administered every 6 hours following the “sensitive” dose of the supplemental insulin scale protocol.

Basal Insulin adjustment.

- Daily basal (glargine U300 and U100) insulin dose will be adjusted as follow:

- If the fasting and pre-dinner BG is between 100 - 140 mg/dl in the absence of hypoglycemia the previous day: no change
- If the fasting and pre-dinner BG is between 141 - 180 mg/dl in the absence of hypoglycemia: increase basal insulin by 10% every day
- If the fasting and pre-dinner BG is 181- 299 mg/dl in the absence of hypoglycemia the previous day: increase basal insulin (glargine) dose by 20% every day
- If the fasting and/or pre-dinner BG is ≥ 300 mg/dl in the absence of hypoglycemia the previous day: increase basal insulin (glargine) dose by 30% every day
- If the fasting and pre-dinner BG is between 70 - 99 mg/dl in the absence of hypoglycemia: decrease TDD (basal and prandial) insulin dose by 10% every day

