Withdrawal criteria	x	x	x	x	x	x	x	x	x	x
Dose adjustment		x	x	x	x	x	x	x	x	x
Efficacy										
Vital signs ¹	x									x
Phys Exam ¹	x									x
Body weight	x									x
BMI	x									x
HbA1c	x									
Fasting BG	x	x	x	x	x	x	x	x	x	x
Pre-meal BG	x	x	x	x	x	x	x	x	x	x
Safety										

Adv events	x	x	x	x	x	x	x	x	x	x
Hypoglycemia	x	x	x	x	x	x	x	x	x	x
Urine pregnancy test	x									x
Trial material										
Drug dispense ²	x									

¹At time of study enrollment and hospital discharge ²As needed

Flow Chart: Aim 2, Outpatient Study

Visit Type	Hospital Day 1	TC	Clinic visit	TC	TC	TC	Clinic visit
Visit #	1	2	3	4	5	6	7
Time-wks	0	2	4	6	8	10	12
Inf. consent	x						
Incl/excl criteria	x						
Randomization	x						
Withdrawal criteria		x	x	x	x	x	x
Drug Compliance		x	x	x	x	x	x
Dose adjustment		x	x	x	x	x	x
Efficacy							
Vital signs	x		x				x
Phys Exam	x		x				x
Body wgt	x		x				x
BMI	x		x				x
HbA1c	x		x				x
Fasting BG	x		x				x
Safety							
Adv events	x	x	x	x	x	x	x
Hypoglycemia	x	x	x	x	x	x	x
Urine pregnancy test	x		x				
CMP or BMP	x		x				x
Trial material							
Drug dispense	x		x				
Drug account	x		x				x

IX. Potential Risks to the Subject:

IX.a. Hypoglycemia. It is possible that following the proposed protocol, patients receiving insulin glargine U300 and U100 may develop hypoglycemia. The risk of hypoglycemia in non-ICU patients treated with subcutaneous insulin is between 5–30% (12, 17, 41, 42). The number of hypoglycemia will be analyzed statistically. For the purpose of this analysis, hypoglycemia is defined as a BG < 70 mg/dL. Severe hypoglycemia is defined as BG < 40 mg/dL.

X. Protection against risks:

We will follow safeguards to minimize the risk to our subjects: a) we will carefully monitor capillary BG at the bedside using a hand-held glucose meter, b) only experienced nurses/or phlebotomist will draw blood samples, and c) women of reproductive age who are sexually active will undergo a urine pregnancy tests prior to participation in the study. To prevent significant clinical events, no patients with history of significant liver, renal impairment or cardiac failure will be recruited in this study.

X.a. Hypoglycemia: We expect that approximately 10% in the inpatient setting and ~20% in the outpatient (post-discharge) arm will experience one or more episodes of hypoglycemia. To minimize the risk of hypoglycemia, the starting dose will be reduced in the basal bolus insulin regimen (TDD: 0.3 units

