per kg of body weight) in patients ≥ 70 years of age and/or eGFR < 60 ml/min. To avoid hypoglycemia, the total daily dose of insulin will be decreased by 10% for BG between 70-99 mg/dl and by 20% after each episode of hypoglycemia (BG < 70 mg/dl). In addition, in patients treated with insulin at home, the TDD of insulin will be reduced by 20% on admission and the attending physician may further reduce insulin dose in the presence of severe hypoglycemia.

Hypoglycemia will be treated with dextrose infusion. Dextrose 50% solution will be given for glucose values < 70 mg/dl. If the patient is awake, 25 ml (1/2 amp) will be given IV or oral juice/snack (crackers) as per protocol. If the patient is not awake: 50ml (1 amp) will be given STAT. Blood glucose levels will be repeated in 15 minutes and dextrose administration will be repeated as needed for values < 70 mg/dl.

XI. Inclusion of women.

We anticipate that ~50% of the study subjects will be female. Absence of pregnancy must be demonstrated by blood or urine testing prior to randomization (in female subjects of child bearing potential only). Glargine U300 and U100 have not been approved during pregnancy.

XII. Inclusion of minorities.

Patients will not be excluded based on race or ethnic origin. We anticipate that approximately one-third of patients will be African Americans, Hispanics, and Caucasians.

XIII. Inclusion of children.

No patients under the age of 18 will be recruited in this study.

XIV. Payment for participation.

Participation in this study is voluntary. Patients will receive one hundred dollars (\$100.00) during the hospital stay. If a participant should stop participation before completion, the payment will be prorated at \$10.00 per day. Participants will receive seventy- five dollars (\$75.00) after each clinic visit at 1 and 3 months after discharge. Total compensation will be two hundred and fifty dollars (\$250.00).

XV. Financial conflict of interests.

This study receives support from Sanofi. [name] serves as a consultant to Sanofi and receives compensation for these services. The terms of this arrangement have been reviewed and approved by Emory University in accordance with its conflict of interest policies.

XVI. Pharmacovigilance specifications

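### The 0.3 U/kg starting-dose safeguard for age ≥70 and/or eGFR <60 has a different patient scope in X.a, IV.d and IV.f, so the text supports more than one starting dose for older or low-eGFR prior insulin users

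*Combined protocol and SAP*

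**What the plan says.** Section X.a (Hypoglycemia), within the section on protecting subjects, states that "the starting dose will be reduced in the basal bolus insulin regimen (TDD: 0.3 units", counted for each kilogram, and applies this to anyone aged 70 or over or with an eGFR below 60. It does not say whether prior insulin use matters. Two sentences later, introduced as a further measure, it says that "in patients treated with insulin at home, the TDD of insulin will be reduced by 20% on admission", with no glucose condition.

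Section IV.d (Basal Bolus Insulin Protocol) says that "subjects treated with insulin prior to admission will receive 80% of the total daily outpatient insulin dose given", again with no glucose condition. It then gives the insulin-naive starts of 0.4 and 0.5 U/kg/day. The 0.3 U/kg/day rule for age or GFR follows directly, worded for patients in general.

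Section IV.f (Treatment Protocol) has two separate lists. For prior insulin users it says "Randomization BG <200mg/dl-give 80% of the TDD" and "Randomization BG>200mg/dl-give 100% of the TDD", with no step for age or renal function. The second list is headed "Insulin Naïve Patients Treated with Oral Agents or GLP1-RAs Prior to Admission", and only there does one find "Reduce TDD to 0.3 units per kg in patients ≥ 70 years of age and/or with an eGFR < 60 ml/min".

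**The concern.** An investigator who starts treatment in a home-insulin user aged 70 or over, or with eGFR 30-59, needs one starting dose. X.a taken at its word, IV.d and IV.f do not give the same answer.

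Three features of the trial make this worth settling. Hypoglycemia is named in Aim 1 and is a secondary outcome in IV.c. Prior insulin use (yes/no) is the randomization factor in IV.e, so the affected patients all sit in one stratum, although they are only part of it. Several institutions (section VII) will dose from this text. Section X.a also tells a reader who is judging risk which protections are in force, and for some patients the detailed treatment protocol does not deliver what it describes.

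**Working it through.** The point rests on no sample size, power or event figure, so there is no statistical result to reproduce. The check is a comparison of the sections, followed by simple arithmetic on the size of the difference.

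**Step 1: the three sections side by side.**

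| Section | Who the 0.3 U/kg rule covers | Start for a prior insulin user |
|---|---|---|
| X.a | Age ≥70 and/or eGFR <60; no limit by prior insulin | Home TDD cut by 20%, no glucose condition; how this combines with 0.3 U/kg is not stated |
| IV.d | Same ages and GFR; follows the insulin-naive doses but is worded for patients in general | 80% of home TDD, no glucose condition |
| IV.f | Insulin-naive list only | 80% of home TDD below 200 mg/dL, 100% above; no age or eGFR step; exactly 200 not assigned |

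**Step 2: can these patients be enrolled?** Yes. VI.b sets no upper age limit, and VI.c excludes only eGFR below 30, which leaves 30-59. Section X says generally that significant renal impairment will not be recruited, but it gives no threshold, and X.a itself writes a rule for eGFR below 60. The age group is not touched by that statement.

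**Step 3: how far apart are the doses if X.a's 0.3 U/kg applies to prior insulin users?** Let h be home TDD in U/kg/day. The documents do not give h; I assume 0.2 to 1.0.

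- IV.f start: 0.80 × h (below 200 mg/dL) or 1.00 × h (above 200 mg/dL).
- Break-even with 0.3 U/kg: 0.3 / 0.80 = 0.375 and 0.3 / 1.00 = 0.30 U/kg/day.

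| h | 80% start | Ratio to 0.3 | 100% start | Ratio to 0.3 |
|---|---|---|---|---|
| 0.2 | 0.16 | 0.53 | 0.20 | 0.67 |
| 0.3 | 0.24 | 0.80 | 0.30 | 1.00 |
| 0.375 | 0.30 | 1.00 | 0.375 | 1.25 |
| 0.4 | 0.32 | 1.07 | 0.40 | 1.33 |
| 0.6 | 0.48 | 1.60 | 0.60 | 2.00 |
| 1.0 | 0.80 | 2.67 | 1.00 | 3.33 |

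The direction depends on the home dose. Below break-even, a fixed 0.3 U/kg would be more insulin than IV.f gives.

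**Step 4: what remains if X.a is read as one rule per group?** Then X.a's measure for home-insulin users is the 20% cut, a start of 0.80 × h. Below 200 mg/dL, IV.f agrees. Above 200 mg/dL, IV.f gives 1.00 × h, a ratio of 1.00 / 0.80 = 1.25 whatever the home dose. On this reading too, the older or low-eGFR prior insulin user above 200 mg/dL does not receive the protection that X.a describes.

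**The case against.** The strongest reply is that X.a is a summary and should be read as one rule per group. The only weight-based starts in the protocol are 0.4 and 0.5 U/kg, both for insulin-naive patients, so a reduction to 0.3 fits them. Home-insulin users have their own sentence in X.a. The table supports this reading: at low home doses 0.3 U/kg would be an increase, which does not fit a sentence about reducing the dose. This is a fair reading and it narrows the conflict. It does not remove it, because of Step 4 and because neither X.a nor IV.d states the limit.

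A second reply is that any difference is short-lived: the primary outcome uses glucose values after the first day of therapy, and doses are adjusted daily. That stands in part. However, the first-day exclusion is stated for the primary outcome only; the hypoglycemia outcomes in IV.c carry none, and the inpatient flow chart records hypoglycemia from day 1. The upward basal steps in IV.f are also percentages of the current dose. Closing a twofold gap in basal dose by 20% steps alone takes four days (1.2³ = 1.73, 1.2⁴ = 2.07), if glucose calls for that step each day.

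A third reply stands in full: the starting rule is the same in both arms, and allocation is blocked by prior insulin use at each institution. The inconsistency does not by itself bias the treatment comparison. The trial is open label, so equal application in both arms is not guaranteed, but nothing in the documents shows unequal application.

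**Conclusion.** The scope of the age/eGFR rule is inconsistent across X.a, IV.d and IV.f, and this should be corrected. The firmest part is at randomization glucose above 200 mg/dL, where IV.f gives an older or low-eGFR prior insulin user neither of the reductions in X.a.

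Several stronger conclusions might be inferred, and the documents do not support them:

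- **That the treatment sections plainly restrict the rule to insulin-naive patients.** IV.f does; IV.d is ambiguous.
- **That prior insulin users lose their stated safeguard altogether.** X.a gives them a 20% cut, and IV.f delivers it below 200 mg/dL.
- **That the day-1 difference is a particular multiple, such as 2.5-fold.** That figure needs an assumed home TDD of 0.75 U/kg/day (0.75 / 0.3 = 2.5) and the 100% rule, so it also contains the separate 80% versus 100% conflict, which concerns all prior insulin users. Over the assumed 0.2-1.0 U/kg/day, the ratio of the IV.f start to 0.3 U/kg runs from 0.53 to 3.33.
- **That a whole stratum is affected or that sites will diverge.** Only the older or low-eGFR members of the stratum are concerned, their share is not given, and sites may or may not dose differently.

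The harm is therefore an inaccurate statement of risk protection and possible inconsistent dosing in a group the protocol itself marks for caution, not demonstrated bias. I take no view on which dosing rule is right.

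**What to change.** Reconcile IV.d, both IV.f lists and X.a so that all state the same patient scope for the age/eGFR rule, and state how that rule relates to the rule for prior insulin users. In the same edit, make the prior-insulin rule agree across the three sections and assign a glucose of exactly 200 mg/dL. The clinical investigators decide the content. Whatever they decide should be applied identically in both arms and at all sites.

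The cost is a text clarification and a check of each site's order set. No patients, visits or procedures are added.

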1. DEFINITIONS

Serious adverse event (SAE): any untoward medical occurrence that at any dose:

- Results in death,
- Is life threatening, (Note: the term “life-threatening” refers to an event/reaction in which the patient was at risk of death at the time of the event/reaction; it does not refer to an event/ reaction which hypothetically might have caused death if it were more severe),
- Requires inpatient hospitalization or results in prolongation of existing hospitalization,
- Results in persistent or significant disability/incapacity,
- Is a congenital anomaly/birth defect, or

- Is a medically important event or reaction. Medical and scientific judgment should be exercised in deciding whether other situations should be considered serious, such as important medical events that might not be immediately life-threatening or result in death or hospitalization, but might jeopardize the patient or might require intervention to prevent one of the other outcomes listed in the definition above.

Related Adverse Event, i.e. Adverse Drug Reaction (ADR): There is a reasonable possibility according to the ISS sponsor that the product may have caused the event.

Unexpected Adverse Event, i.e. Adverse Drug Reaction (ADR): An adverse reaction, the nature or severity of which is not consistent with the applicable product information (e.g., Investigator's Brochure for an unapproved investigational medicinal product or package insert/summary of product characteristics for an approved product). An expected ADR with a fatal outcome should be considered unexpected unless the local/regional product labelling specifically states that the ADR might be associated with a fatal outcome.

Adverse Event of Special Interest (AESI): An adverse event of special interest (AESI) is an adverse event (serious or non-serious) of scientific and medical concern specific to the Sponsor's product or program, for which ongoing monitoring and rapid communication by the Investigator to the Sponsor may be appropriate. Such events may require further investigation in order to characterize and understand them. AESIs may be added or removed during a study by protocol amendment.

New safety finding : Any (other than reportable individual case safety report (ICSR)) safety issue that may require expedited reporting because providing information that may lead to a change in the known risk-benefit balance for the product and as mentioned, but not limited to, in the following regulatory texts: Europe: Volume 9A of the Rules Governing Medicinal products in the European Union (September 2008) Section 4.1; and US: FDA: 21 CFR Parts 312 Investigational New Drug Application- Section 312.32, (c) (1) IND safety reports.

2. OBLIGATIONS AND RESPONSIBILITIES OF THE ISS SPONSOR

- The ISS sponsor warrants that the study will be performed in compliance with all applicable local and international laws and regulations, including without limitation ICH E6 guidelines for Good Clinical Practices.
- The ISS sponsor shall be responsible for the respect of all obligations required by applicable local and international laws and regulations.
- The sponsor shall be responsible for ensuring submission of required expedited and periodic reports to the appropriate Regulatory Authority (RA), the Ethics Committee and investigators of each country participating in the ISS (based on applicable regulations).
- Any Periodic reports (e.g. Development Safety Update Report (DSUR)), submitted to Regulatory Authority must first be transmitted to Sanofi for review and comment.
- The study reports of any ISS must contain a section describing safety review and conclusion and must be reviewed by Sanofi before finalization.
- *New Safety Findings in a study pertaining to safety of product must be transmitted within 1 business day. (e.g., Data Safety Monitoring Board recommendations)*

The ISS sponsor must provide to Sanofi upon request results of any relevant complementary exams performed to obtain the final diagnosis of any SAE (e.g., hospital discharge summary, autopsy, consultation).

- The Institution must report the following information in English to the Sanofi group entity Pharmacovigilance contact:

- Routine transmission of all Serious Adverse Events (SAEs) including pregnancy, overdose and Adverse Events of Special Interest (AESI), if any. These events must be transmitted within 1 business day of the Institution's awareness or identification of the event.
 - Routine transmission of SAEs related to the use of the Sanofi product must be transmitted within 1 business day of the Institution's awareness or identification of the event. The reference safety information to be used by the Institution for evaluation of expectedness of adverse events shall be the current approved product label available in the country *for an approved indication or the Investigator Brochure for an unapproved indication*.
 - Any Periodic reports (e.g. Development Safety Update Report (DSUR)), submitted to Regulatory Authority must be transmitted to Sanofi at the time of submission.
 - *New Safety Findings* in a study pertaining to safety of product must be transmitted within 1 business day. (e.g., Data Safety Monitoring Board recommendations)
 - The study reports of any ISS must contain a section describing safety review and conclusion and must be reviewed by Sanofi before finalization.
- *The reference safety information to be used by the ISS sponsor for evaluation of expectedness of adverse events shall be the current approved product label available in the country (for an approved indication)*

****Check appropriate column and cross out other columns**

BG (mg/dL) Insulin Sensitive Usual Insulin Resistant

BG (mg/dL)	No sliding scale (supplemental)insulin		
< 141			
141 – 180	2	3	4
181 – 220	3	4	6
221 – 260	4	5	8
261 – 300	5	6	10
301 – 350	6	8	12
351 – 400	7	10	14
> 400	8	12	16

BEDTIME sliding scale: Supplemental Sliding Scale Insulin dose at bedtime starting at BG > 220 mg/dL

BG (mg/dL) Insulin Sensitive Usual Insulin Resistant

BG (mg/dL)	No sliding scale (supplemental) insulin		
< 220			
221 – 260	1	2	4
261 – 300	2	3	5
301 – 350	3	4	6
351 – 400	4	5	7
> 400	5	6	8

The numbers in each column indicate the number of units of glulisine insulin *per dose*. Supplemental” dose is to be added to the scheduled dose of aspart insulin. If a patient is able and expected to eat all or most of his/her meals, supplemental insulin will be administered before each meal following the “usual” column dose. Supplemental insulin at bedtime = half of premeal insulin dose. Example, a patient with blood glucose of 260 mg/dl will receive 5 U before a meal or 2 U at bedtime of supplemental insulin. If a patient is not able to eat (NPO), supplemental insulin will be administered every 6 hours (6-12-6-12) following the “sensitive” column dose. Example, a patient kept NPO with blood glucose of 200 mg/dl will receive 3 U of supplemental insulin.

The patient’s inpatient primary medical or surgical team may change insulin dose at their discretion in the presence of hypoglycemia (BG <70 mg/dL) or severe hyperglycemia (BG >350 mg/dL). In addition, the attending physician may consider using the total supplemental insulin dose, patient’s nutritional intake, and results of BG testing to adjust insulin regimen.

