Randomized multi-center trials have shown that basal bolus treatment with glargine U100 improve glycemic control and reduce the rate of hospital complications compared to sliding scale regular insulin (SSI) (12-14). In general surgery patients, the basal bolus approach results in significant reduction in a composite of hospital complications including postoperative wound infection, pneumonia, bacteremia, and acute renal and respiratory failure (15). The hospital hypoglycemia rate was reported in 3% in medicine (16) and 12% in surgery (17) patients treated with basal bolus regimen. Based on these results, clinical practice guidelines have recommended the use of basal bolus approach as the preferred insulin regimen for the management of non-ICU patients with diabetes (18-20).

The Food and Drug Administration and the European Commission recently approved Glargine U300 insulin for the treatment of patients with diabetes. Glargine U300 is long-acting insulin with duration of action longer than 24 hours (21, 22). The results of the Edition clinical trials with more than 3500 patients demonstrated that glargine U300 resulted in similar improvement in glycemic control and with a lower rate of nocturnal hypoglycemia compared to glargine U100 (23-27). The efficacy and safety of glargine U300 has been documented in patients with type 1 and type 2 diabetes (22-27); however, no previous studies have assessed the safety and efficacy of these new formulations in the inpatient (hospital) setting. In addition, certain features of glargine U300 needs to be investigated in the hospital including 1) prolonged duration of action, which may limit the ability to make day-to-day adjustments in insulin dosage; 2) a steady-state insulin concentration achieved after second or third day of therapy; and limited safety data in acutely ill patients with altered nutritional status. Accordingly, the present randomized clinical trial will compare the efficacy and safety of a basal bolus regimen with glargine U300 and glargine U100 (standard of care) in general medicine and surgery patients with T2D.

B. Specific Aims:

Aim 1. To determine differences in inpatient glycemic control, as measured by mean daily blood glucose concentration and frequency of hypoglycemia, in general medicine and surgery patients with T2D treated with basal bolus regimen with glargine U300 and U100 plus glulisine insulin before meals.

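### Scheduled mealtime glulisine for an inpatient who can eat but eats poorly is held under section IV.d and given under section IV.f; the intake terms need reconciling with Appendix 1

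*Combined protocol and SAP*

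**What the plan says.** **Scheduled glulisine.** Section IV.d (Basal Bolus Insulin Protocol) states: "Patients with poor oral intake or to be kept NPO will receive the basal dose, but prandial dose will be held". Section IV.f (Treatment Protocol) sets the rule separately for two groups. For patients on insulin before admission it reads: "Glulisine insulin will be given in three equally divided doses before each meal. To prevent hypoglycemia, if a subject is not able to eat", in which case the dose is held. For insulin-naive patients it likewise says that "if a subject is not able to eat, the dose of glulisine will be held". Section IV.f does not mention poor intake in either place.

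**Supplemental glulisine.** Section IV.f has two states. In the first, "If a patient is able and expected to eat most of his/her meals, supplemental insulin will be administered before meals and at bedtime", using the usual column. In the second, the patient cannot eat and is dosed every 6 hours from the sensitive column. Appendix 1 repeats the pair. For the first: "If a patient is able and expected to eat all or most of his/her meals, supplemental insulin will be administered before each meal", usual column. For the second: "If a patient is not able to eat (NPO), supplemental insulin will be administered every 6 hours (6-12-6-12) following the" sensitive column. Appendix 1 also lets the attending physician take nutritional intake into account when adjusting the regimen.

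**Context.** Sections IV.d and IV.f put half of TDD into glulisine, split over three meals. Section IV.e states that the trial is open label.

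**The concern.** Three intake states arise on a ward: the patient eats most meals, eats but poorly, or is NPO. The first and last are handled alike throughout. The middle one is not. A nurse or investigator working from IV.d would hold that patient's mealtime dose; one working from IV.f would give it.

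IV.f itself gives prevention of hypoglycemia as the reason for holding the dose, so the plan accepts that the choice bears on safety. It can also move glucose the other way when the dose is withheld. Glucose below 70 mg/dl is a secondary outcome and mean daily glucose is the primary one. With several sites and no blinding, similar patients could be treated differently according to which section the site follows. Reduced intake is also not remote from the trial's purpose: among the reasons for studying U300 in hospital, the introductory section lists "limited safety data in acutely ill patients with altered nutritional status".

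**Working it through.** **Step 1. Set the rules side by side.**

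| Intake state | Scheduled glulisine, IV.d | Scheduled glulisine, IV.f | Supplemental, IV.f and Appendix 1 |
|---|---|---|---|
| Eats most meals | Given | Given | Usual column, before meals and at bedtime |
| Eats, but poorly | Held | Given by default; no exception applies | No state named; physician discretion (Appendix 1) |
| NPO | Held | Held | Sensitive column, every 6 hours |

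**Step 2. Can the two scheduled-dose rules be read as one?** They agree if inability to eat in IV.f includes poor intake. Two features of the text count against that. IV.d lists poor intake and NPO as separate states. Appendix 1 puts NPO in brackets after the same phrase that IV.f uses. Read literally, the rules diverge for the middle row.

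**Step 3. Size for scheduled insulin.** Basal = TDD/2 and prandial = TDD/2, so each meal dose = TDD/6.

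- All mealtime doses held: TDD/2. All given: TDD. Ratio = 2.
- Starting TDD for insulin-naive patients is 0.3, 0.4 or 0.5 U/kg/day. Body weight is not in the documents; 70 to 100 kg is assumed.
- Lowest case: 0.3 × 70 = 21 U/day given against 10.5 U/day held; 21/6 = 3.5 U per meal.
- Middle dose: 0.4 × 70 = 28 against 14 U/day; 0.4 × 100 = 40 against 20 U/day.
- Highest case: 0.5 × 100 = 50 against 25 U/day; 50/6 = 8.3 U per meal.
- For patients already on insulin, TDD starts from 80% or 100% of the home dose. The half-and-half split is the same, so the ratio is again 2.

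Two-fold is an upper figure. If only one meal is affected, the contrast is TDD against TDD × (1 − 1/6) = 0.833 TDD, a ratio of 1.2. Upward titration in IV.f raises basal alone. After one 20% basal increase the contrast is (0.6 + 0.5) = 1.1 against 0.6 of the starting TDD, a ratio of 1.83.

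**Step 4. Size for supplemental insulin.** The worked examples in Appendix 1 reproduce from its tables: at 260 mg/dl the usual column gives 5 U before a meal and 2 U at bedtime; at 200 mg/dl the sensitive column gives 3 U when NPO.

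For a patient in neither named state, the two candidate schedules are compared over a day. Glucose is assumed to stay in one band, and the before-meal table is assumed to apply to all four 6-hourly doses.

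| Glucose, mg/dl | Usual: 3 × meal + bedtime | Sensitive: 4 × dose | Difference, U/day |
|---|---|---|---|
| 141–180 | 3 × 3 + 0 = 9 | 4 × 2 = 8 | 1 |
| 181–220 | 3 × 4 + 0 = 12 | 4 × 3 = 12 | 0 |
| 221–260 | 3 × 5 + 2 = 17 | 4 × 4 = 16 | 1 |
| 261–300 | 3 × 6 + 3 = 21 | 4 × 5 = 20 | 1 |
| 301–350 | 3 × 8 + 4 = 28 | 4 × 6 = 24 | 4 |
| 351–400 | 3 × 10 + 5 = 35 | 4 × 7 = 28 | 7 |
| Above 400 | 3 × 12 + 6 = 42 | 4 × 8 = 32 | 10 |

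The daily totals are nearly equal up to 300 mg/dl; mainly the timing differs. The scheduled-dose conflict is much the larger matter.

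**The case against.** The best defence is that there are not two opposing instructions. Only IV.d speaks about poor intake. IV.f is silent on it, and IV.d is offered as a brief summary of the regimen. A sensible clinician would let the explicit statement fill the silence, or would read inability to eat as covering inadequate intake. The bracketed NPO that counts against that reading sits in the supplemental-scale text, not in the scheduled-dose rule. Part of this stands: the conflict arises from the default in IV.f, not from an express order to dose poor eaters. It does not remove the problem. IV.f is the detailed treatment section, its default is to give the dose, and its only stated exception, on the wording of Appendix 1, does not reach this patient.

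The second defence is that clinician judgement is written into the plan. Appendix 1 has one column marked per patient and lets the attending physician weigh nutritional intake. This largely answers the supplemental gap: the middle state is left to stated discretion, at little cost in dose up to 300 mg/dl. For the scheduled dose it is weaker, since permission to adjust does not say which rule is the starting point.

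Third, the basal rule does not share the conflict. IV.d gives basal insulin in both poor intake and NPO, so it leaves no conflict over basal insulin for the poor eater. The discrepancy concerns background glulisine, worded identically for both arms. Between-site variation is partly handled in analysis: the mixed model may include centre, and the Cochran-Mantel-Haenszel test adjusts for it. All of this stands as regards the treatment comparison. None of it settles what is given at the bedside.

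**Conclusion.** The inconsistency is real and should be corrected. For a patient who can eat but eats poorly, IV.d holds scheduled glulisine, while IV.f, read with Appendix 1, gives it. Over a full day at the starting dose, scheduled insulin can differ up to two-fold: 10.5 against 21 U/day to 25 against 50 U/day, over the stated starting doses and an assumed 70 to 100 kg. This rests on the literal reading of inability to eat as NPO, and on all three meals being affected before any basal-only increase. The supplemental gap is secondary.

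The documents do not support three stronger inferences that a reader might draw.

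- **That open-label staff will dose the arms differently and bias the comparison.** This is possible, but the wording is the same for both arms and no effect on mean daily glucose or hypoglycemia is shown.
- **That poor eaters are precisely the patients for whom the plan doubts U300.** Altered nutrition is one of several listed concerns, the others being duration of action and time to steady state. It also covers NPO patients, who do have rules.
- **That many patient-days are affected.** The documents give no figure for the share.

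This is therefore a point of safety and treatment consistency, not a threat to the validity of the non-inferiority comparison.

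**What to change.** Reconcile section IV.d (Basal Bolus Insulin Protocol), section IV.f (both patient groups and the supplemental-insulin paragraph) and Appendix 1. Define the intake states once, use the same terms in all three places, and map each state to one scheduled-glulisine rule and one supplemental rule (column and schedule). If the middle state is meant to stay with the attending physician, say so where the scheduled dose is set as well as in the appendix. Which rule applies to which state is for the sponsor's clinical team; this review takes no view.

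The cost is a wording change to the protocol and the order sheet, with no extra patients or procedures. Recording intake state each hospital day and tabulating it by arm would let the trial describe how the rule was applied. That is optional, at the price of one daily data field.
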